7.0 Study Endpoints*

PROTOCOL TITLE: Optimization of 25(OH) vitamin D levels in African Americans

Primary Endpoints: Blood levels of 25(OH)VD, TNF- α , and HOMA-IR.

Safety Endpoints: Serum calcium (Ca²⁺), PTH, liver, and kidney function tests will be carried out at visits 0, 2, 4, and 6. Whole blood CBC and pregnancy tests will be done at all visits.

Secondary Endpoints: Blood levels of 1,25(OH)₂VD, HbA_{1c}, and pro-inflammatory and anti-inflammatory cytokines (such as IL-2, IL-6, and IL-10).

We will also perform tests to monitor liver and kidney function tests at each visit and complete blood count analyses for any sign of any anemia or unexpected changes in white or red blood cell profiles.

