10.0 Data Management* and Confidentiality

Analyses of data will be performed by the biostatistician, [name]. A *p*-value of less than 0.05 for a statistical test will be considered significant. Data will be analyzed statistically to compare the 4 groups at baseline and various visits using ANOVA. The Wilcoxon signed-rank or paired *t*-test will be used to determine significant changes after supplementation for each treatment group, and the ANOVA test to compare the 4 treatment groups on changes. The results for the pairwise comparisons among the 4 time points will determine whether there is a significant change in the outcome variables over time. The effect of covariates or possible confounders (age, sex, BMI, initial levels of outcomes, etc.) will be controlled for and tested for their significant effects by including them in the repeated measures model used.

Based on animal studies, co-supplementation with LC+VD will be more successful and raise serum 25(OH)VD levels by nearly 30 ng/mL(17, 18). Our goal is to raise circulating 25(OH)VD levels by an average of 30 ng/mL, and reduce IR levels by 35% in all AA subjects receiving combined VD+LC supplementation. To observe a significant response or change, a sample size of 7 for 25(OH)VD, and 27 for IR were considered adequate using a paired *t*-test conducted at 5% level of significance and 80% power. We chose a goal of 30 subjects in each group who complete the study in the VD+LC supplementation and other groups. Based on our experience from a previously completed clinical trial (H-09-073), enrollment of and consent from 160 AA volunteers who participate in blood collection for screening should give us more than the required sample size of 30 subjects in each group (120 in 4 groups) after factoring in a dropout rate of about 16% for screen failures, withdrawal before randomization, or those who did not complete all the visits. Our experience also suggests that nearly 190 subjects will need to be contacted to achieve our goal of 160 AA volunteers who complete the written consent form and are enrolled in this clinical trial. This takes into account the fact that only about 85% of those initially contacted will indeed show up for the screening visit and complete the written informed consent.

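### The rule for declaring change over time rests on six pairwise tests at 0.05 each, which gives about a 20% false-declaration rate if any one significant pair counts

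*Protocol*

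**What the plan says.** Everything on this point stands in Protocol section 10.0.

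- Threshold, set per test: "A *p*-value of less than 0.05 for a statistical test will be considered significant".
- Rule for change over time: "The results for the pairwise comparisons among the 4 time points will determine whether there is a significant change in the outcome variables over time".
- Within-arm change has its own sentence: "The Wilcoxon signed-rank or paired *t*-test will be used to determine significant changes after supplementation for each treatment group".
- Comparison of arms is also separate: "the ANOVA test to compare the 4 treatment groups on changes".
- A repeated measures model appears only as the place where covariates are handled: "by including them in the repeated measures model used".

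The section does not list the four time points. Section 3.0 gives five clinic visits, and section 6.0 makes V-1 the screening visit and V0 the baseline after the run-in. Section 7.0 says of the safety tests: "liver, and kidney function tests will be carried out at visits 0, 2, 4, and 6". The four points are therefore most plausibly V0 and three on-treatment visits. That is an assumption, but the six-pair error rate does not depend on which four visits are meant.

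**The concern.** The sentence gives the pairwise results the deciding role. Combined with a threshold that applies to each test on its own, the natural way to follow it is to run six tests and report a change if one of them is significant. Six chances at 5% do not make a 5% rule.

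Three of the six pairs compare two on-treatment visits. They can describe a time course or a plateau, but they do not measure change from the pre-treatment baseline, so part of the excess error comes from pairs that do not address whether supplementation moved the outcome from V0.

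At stake is the reliability of statements that 25(OH)VD, TNF-α or HOMA-IR changed over time. These are the three primary endpoints in section 7.0.

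**Working it through.** **The plan's own figures.** Section 10.0 states no family-wise error rate, so there is none to reproduce. Its only computed figures here are the paired t-test sample sizes, 7 for 25(OH)VD and 27 for IR, at the 5% level and 80% power. They cannot be reproduced because no SD is given. Read as two-sided, they imply a standardised change of about 1.27 to 1.43 (SD of change about 21 to 24 ng/mL for a 30 ng/mL rise) and about 0.56 to 0.57. Nothing below depends on them.

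**Inputs.** Four time points and a per-test level of 0.05 (section 10.0); 30 completers per arm (section 10.0). Assumed: no true change, two-sided tests, and any significant pair counts as a change. The correlation between visits is not given, so a range is used.

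**Number of pairs.** 4 × 3 / 2 = 6. Three involve baseline and three do not.

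**Analytic check.** With a pooled error term and equal correlation, the chance that at least one of six unadjusted tests is significant is P(Q₄ > √2 × t₀.₉₇₅), where Q₄ is the studentised range of four means.

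- One arm of 30, 29 × 3 = 87 df: 20.1%.
- Four arms of 30 pooled, (120 − 4) × 3 = 348 df: 20.3%.

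The rate is thus about 20% under either reading of the sentence; only the number of families differs.

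**Simulation.** Six paired t-tests, n = 30, 100,000 replicates per setting:

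| Correlation between visits | Any of six pairs | Any of three contrasts with baseline | Six pairs, Bonferroni |
|---|---|---|---|
| Equal, 0.3 | 20.7% | 12.5% | 4.3% |
| Equal, 0.7 | 20.8% | 12.6% | 4.3% |
| AR(1), 0.5 | 20.1% | 11.8% | 4.1% |
| AR(1), 0.7 | 19.6% | 11.3% | 4.0% |
| AR(1), 0.9 | 18.9% | 11.1% | 3.8% |
| AR(1), 0.98 | 18.7% | 10.9% | 3.7% |

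The independence formula, 1 − 0.95⁶ = 26.5%, is too high here because the six differences share time points. A single contrast of the final visit with baseline gives 5% by construction.

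**Share due to on-treatment pairs alone.** At equal correlation 0.3: 20.7% − 12.5% = 8.2%. About 8% of null outcomes would be declared changed with no significant contrast against baseline.

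**Effect of adjusting.** Bonferroni uses 0.05 / 6 = 0.0083 per pair and gives 3.7% to 4.3%. A Tukey-type adjustment uses about 0.0104 per pair on 87 df and holds 5% under equal correlation.

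**The case against.** **The protocol does not say the tests are unadjusted.** This is true. A 0.05 threshold is compatible with adjusted p-values, and choice of adjustment is often left to an analysis plan, which may exist here. But the section does more than stay silent: it sets the threshold for each test and lets the pairwise results decide. A later plan that adjusted or gated would be repairing that rule. An overall time test required beforehand would bring the rate to about 5% when nothing changes at any visit; none is stated.

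**The any-pair reading is supplied by the reader.** This also stands. The sentence does not say how six results combine into one conclusion, so the 20% is conditional on that reading. It is the simplest way to carry out the sentence, and no other is offered.

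**Stronger readings that the documents do not support.**

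- A reader might multiply over arms: 1 − (1 − 0.206)⁴ = 0.60 for a false change in at least one of four arms. This needs within-arm contrasts, and the sentence names no arm. It also needs all four arms to be null, whereas section 2.0 reports that VD raises 25(OH)VD and that LC lowers TNF-α and IR. With two null arms the figure is 1 − 0.794² = 0.37. Even one 5% test per arm gives 1 − 0.95⁴ = 0.185 over four null arms.
- A reader might infer that this rule decides whether VD+LC meets its goals ("Our goal is to raise circulating 25(OH)VD levels by an average of 30 ng/mL", and a 35% fall in IR) and contradicts the sizing. The sizes 7 and 27 come from a paired t-test, which matches the separate sentence on change after supplementation.
- A reader might call any pattern of changed and unchanged arms uninterpretable. That is too strong: arms are compared by ANOVA on changes, which this sentence does not touch.

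**Conclusion.** The concern holds as a poorly fixed rule for declaring change over time. Followed as written, with any significant pair counting, it declares a change in about 20% of outcomes that have none (18.7% to 20.8% over the correlations tried), against a nominal 5%. Counting only contrasts with baseline gives about 12 to 13% under equal correlation and about 11 to 12% under AR(1). The unit is the outcome if arms are pooled, and the arm and outcome if not.

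This rests on three assumptions: no adjustment is applied, one significant pair is enough, and no overall test comes before. The size does not depend on the SD and depends little on the correlation. The between-arm ANOVA on changes, and with it the comparison of VD+LC with VD alone, is unaffected. The point is worth correcting but does not undermine the trial's main comparison.

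**What to change.** Amend the sentence in section 10.0 to one of these rules:

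1. Change over time is judged by the single contrast of the final visit with V0 at 0.05. Contrasts of intermediate visits with V0 are tested only if that one is significant, with Holm adjustment.
2. Change over time is judged by all six pairs with a stated adjustment: Bonferroni, Holm or Tukey-type.

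Either holds the rate at or below about 5% per family. The Tukey-type figure relies on equal correlation between visits; Bonferroni and Holm do not. The first rule keeps the full 5% for the contrast closest to the question of change after supplementation. The second keeps the on-treatment comparisons as formal tests. Treating those as descriptive is a choice, not a requirement.

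In the same sentence, name the four time points and state whether the contrasts are within arm or pooled over arms, since this defines the family.

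The cost is a wording change, with no added visits, assays or subjects. The statistical price is slightly less chance of declaring a change seen only at an intermediate visit (first rule) or in a single pair (second rule). Neither rule controls error across arms or across the three primary endpoints.

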3.0 Inclusion and Exclusion Criteria*

Informed written consent will be obtained from all subjects according to the IRB approved protocol. All subjects in this study will be adult AA volunteers and will meet the inclusion/exclusion criteria given below.

INCLUSION CRITERIA: (1) African-American adults aged 18-65 years willing to participate in 5 clinic visits where blood will be drawn; (2) participants who demonstrate an understanding of the risks and benefits of the protocol and sign the informed consent form; (3) participants willing to complete standard health history questionnaire before and during the study (**Copy enclosed**); (4) women with negative pregnancy tests (pregnancy test will be performed on all women participants)

EXCLUSION CRITERIA: (1) History of cardiovascular disease, sickle cell disease, or metabolic disorders including: diabetes, uncontrolled hypertension, hypothyroid, or hyperthyroid; (2) any sign of hepatic dysfunction or renal dysfunction, hypercalcemia, or nephrolithiasis; (3) those taking antiepileptic medications, glucocorticoids, or weight loss or other dietary supplements within the two months previous to enrollment or during the study; (4) those who visit tanning booths; (5) any subject who develops an infection and has to take antibiotics; and (6) women with positive pregnancy tests or those who are nursing. (7) adults unable to consent or prisoners. Any subject taking vitamin D or any other vitamin

PROTOCOL TITLE: Optimization of 25(OH) vitamin D levels in African Americans

or herbal supplement even advised by a doctor or over-the-counter will not be enrolled in the study.

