5.0 Multi-Site Research* N/A (This is only site)

6.0 Study Timelines*

Potential subjects will be contacted over phone or potential subjects may call in response to advertisement and agrees to participate in this study will be asked to come to the clinic after fasting overnight. Fasting blood will be collected after written informed consent. Blood collected at V₋₁ will serve as the sample for the screening visit for the clinical trial. Subjects meeting the inclusion/ exclusion criteria will continue in the clinical trial. All subjects will fill out the complete standard health history before the study and at each visit during the study. This clinical trial will be registered at the ClinTrial.gov site.

Initially, all of the study subjects will be provided placebo supplementation as a placebo run-in period for one month before randomization. Visit 2 (V₀) is for obtaining baseline levels after the run-in period. AA-subjects will be block randomized into four groups. Members of the groups will ingest capsules containing placebo and supplements, orally, daily: (I) placebo (P); (II) LC (1000 mg); (III) VD (2000 IU); (IV) VD and LC. Each capsule will contain a placebo or cholecalciferol (2000 IU) or LC (1000 mg). Placebo group will take two placebo capsules a day in the morning; II LC group will receive two capsules of LC daily; (III) VD group will take two capsules and each capsule will contain 1000 IU VD daily; (IV) VD+LC group will take daily two capsule containing 1000 IU+500 mg LC. Supplements will be taken daily with food at breakfast for 6 months, while participants continue to carry on a normal lifestyle. During the placebo run-in period, all subjects will also take two placebo capsules daily. Based on previous experience, we expect a dropout rate of about 16% as a result of non-compliance, lost contact, taking another medicine, or a subject found to have another disorder. We expect that at least 30 subjects in each group will complete the study. Overnight fasting blood will be collected at each visit. Also, anthropomorphic data, body weight, and height (BMI), the record of any drug use, any adverse effects/complaints (related or unrelated), and Questionnaire will be collected at each visit by the nurse. It is likely to require ~90 minutes to collect the subject's history and other data in interviews with the nurse/dietician and investigators.

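### The within-arm paired test of 25(OH)VD runs over about six months with no calendar term, so if entry is concentrated in one part of the year, season alone can produce a significant change in any arm

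*Protocol*

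**What the plan says.** Section 7.0 makes 25(OH)VD a primary endpoint ("Primary Endpoints: Blood levels of 25(OH)VD", listed with TNF-α and HOMA-IR). Under section 6.0, baseline is the visit after the one-month placebo run-in, and then: "Supplements will be taken daily with food at breakfast for 6 months, while participants continue to carry on a normal lifestyle". Section 7.0 labels visits 0, 2, 4 and 6. Read as months, which the six-month treatment period suggests, the first and last draws are about half a year apart.

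Section 10.0 fixes three analyses:

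- A Wilcoxon signed-rank or paired t-test "will be used to determine significant changes after supplementation for each treatment group". The sample sizes of 7 for 25(OH)VD and 27 for insulin resistance are derived from the paired t-test.
- An "ANOVA test to compare the 4 treatment groups on changes".
- Control for "age, sex, BMI, initial levels of outcomes, etc", done "by including them in the repeated measures model used".

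Season, month and date of draw appear nowhere. The one item on ultraviolet exposure is in section 3.0, which excludes "those who visit tanning booths". Allocation is by blocks to four concurrent arms, one of them placebo. No accrual period is given.

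**The concern.** By excluding tanning-booth users, the protocol treats ultraviolet exposure as something that can disturb 25(OH)VD. Sunlight varies over the year, and six months is the interval at which a yearly cycle can produce its largest change.

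A paired test within one arm has no control group and no place for a covariate. It cannot tell a supplement effect from a seasonal one, and block randomisation does not help, because no arms are being compared. At stake is a finding of significant change in an arm where the supplement did nothing. In the opposite season, a real rise could be partly masked.

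Between arms the question is only one of precision: season that is left out of the model stays in the error term.

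**Working it through.** **1. The plan's own figure.** The SD of change behind n = 7 is not stated, so that figure can only be solved backwards. For a two-sided 5% paired t-test with 80% power (sidedness is not stated; two-sided assumed), n = 7 is the smallest adequate size when the standardised change lies between 1.27 and 1.43. With a rise of 30 ng/mL, the SD of change is 30/1.43 to 30/1.27, or 20.9 to 23.6 ng/mL from the unrounded values. I use 23.6, which makes the seasonal effect look smallest, and an assumed 10 for comparison.

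**2. Seasonal model (assumed).** Take a yearly cosine of amplitude A around the mean. Two draws six months apart then differ by −2A·cos(2π × date of first draw, in years). The documents give no amplitude; I take A = 2 to 5 ng/mL.

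**3. Within arm, baseline draws spread over one half of the year.** The cosine averages 2/π over that half-year, so the mean shift with no supplement effect is 2A × 2/π = 4A/π. This gives 2.5 ng/mL at A = 2 and 6.4 ng/mL at A = 5, or 8% to 21% of the 30 ng/mL goal. The chance of rejection comes from the noncentral t with 29 df and noncentrality (shift/SD) × √30:

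| A | Shift (ng/mL) | Noncentrality, SD 23.6 | Rejects | Noncentrality, SD 10 | Rejects |
|---|---|---|---|---|---|
| 2 | 2.5 | 0.59 | 9% | 1.39 | 27% |
| 5 | 6.4 | 1.48 | 30% | 3.49 | 92% |

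The nominal rate is 5%. Tighter entry is worse. In simulation with entry over two months around the trough, the placebo paired test rejected in 26% (A = 3) to 58% (A = 5) of trials at SD 23.6.

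**4. Within arm, entry spread over the whole year.** The shift averages to zero. Simulated rejection of the placebo paired test was 2.5% to 5.2% (A = 3 and 5; SD 10 to 23.6), so there is no inflation.

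**5. Between arms, bias.** Four-arm ANOVA on changes, blocks of four assumed, A = 3 and 5, 3,000 runs per setting. Type I error was 0.9% to 4.4% with year-round entry and 4.1% to 5.2% with entry in a single season. It is never inflated beyond simulation error.

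**6. Between arms, precision.** Year-round entry adds variance 2A² to the change. At SD 23.6 that is 8/557 to 50/557, or 1.4% to 9%. At SD 10 it is 8/100 to 50/100, or 8% to 50%.

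These figures ignore the baseline level, which the protocol already names and which carries the season of the first draw. With baseline in the model (30 v 30, year-round entry, assumed stable between-subject SD of 8, 2,000 runs per setting):

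- At SD 20.9 to 23.6, power was 93.9% to 94.6% without season and 93.9% to 94.8% with it: under 1 point gained.
- At SD 8 to 12, season gained about 2 to 14 points, most at SD 8 with A = 5. Simulation error on each power is about √(0.8 × 0.2/2000) = 0.9 points.

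**7. Form of the covariate.** At months 0, 2, 4 and 6 from a peak, the cosine is 1, 0.5, −0.5 and −1, which sums to zero. A single main effect of baseline date moves all four visits by the same amount, so it removes none of this change in the repeated measures model.

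**The case against.** The strongest reply is that nothing has been fixed wrongly. The covariate list is illustrative and open, so season is unnamed rather than excluded, and a statistical analysis plan could add it. The protocol already has concurrent placebo, block allocation and an ANOVA on changes between arms, and it already names the baseline level. The amplitude is not in the documents, and reading a within-arm change as an effect is a weakness of uncontrolled paired tests whatever the season.

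Much of this stands. A reader might infer that the protocol rules season out of the model; it does not. A reader might also infer a substantial loss of between-arm power; at the protocol's implied SD, with baseline adjustment, the loss is negligible. It becomes material only if the true SD of change is far smaller, at 8 to 12.

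What does not fall is the within-arm test. Section 10.0 commits to it and sizes the trial on it, and no covariate list, open or closed, can reach it. The same section also uses comparisons among the four time points to decide whether outcomes change over time, and with concentrated entry time and season cannot be separated.

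**Conclusion.** The point holds for the within-arm tests, conditional on accrual. If entry is concentrated in one half of the year and the seasonal amplitude is 2 to 5 ng/mL, the paired test at n = 30 rejects with no supplement effect in 9% to 30% of trials at SD 23.6, and in 27% to 92% at SD 10. The risk of a false finding is greatest in the placebo and LC arms. A true rise of 30 ng/mL would be significant regardless, though its estimated size would still shift. If the amplitude is near zero, nothing is lost.

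Two stronger readings are not supported. First, the comparison between arms is not biased: arms are randomised in blocks and followed concurrently, so season affects them alike. Second, the two harms do not occur together in full. Year-round entry costs some precision but cancels the within-arm shift; single-season entry shifts the within-arm mean but adds almost no between-arm error. The protocol gives no accrual period, so neither pattern can be assumed or excluded.

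The amplitude, the SDs of 8 to 12, the between-subject SD of 8 and blocks of four are assumptions. That the last visit is at month 6 is inferred. The improvement is minor but worth making.

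**What to change.** 1. State in section 10.0 that the conclusion on supplement effect for 25(OH)VD rests on between-arm contrasts of change: VD+LC against VD, which is the comparison in the stated objective, and against placebo. Label the within-arm paired or Wilcoxon tests descriptive. This is the essential step: with single-season entry, season coincides with visit and no covariate can rescue a within-arm test.
2. Add season to the named covariates for 25(OH)VD. In the repeated measures model, use sine and cosine of each visit's draw date, or of the baseline date interacting with visit. In a change-score ANCOVA, sine and cosine of the baseline date suffice, alongside the baseline level.

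The cost is one or two sentences and a few degrees of freedom: two for sine and cosine, or up to 2 terms × 4 visits = 8 with the interaction. The visit dates must be kept for analysis; the protocol does not say so expressly, but dated visits should supply them. Sample size and visit schedule are unaffected by this point.

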1.0 Objectives*

Two-thirds of the US population, particularly African Americans (AA), is at risk for inadequate or deficient 25-hydroxy-vitamin D (25(OH)VD). Epidemiological studies demonstrate an association between better health outcomes and higher blood levels of 25(OH)VD. Randomized controlled clinical trials have shown that, while supraphysiological high doses of VD are needed to achieve adequate blood levels of 25(OH)VD, not all subjects respond to them. Recent studies have also questioned the therapeutic effects of high-dose VD supplementation. This application presents our design for a randomized, double-blind, placebo-controlled clinical trial to test the hypothesis that supplementation with VD in combination with L-cysteine (LC) is more successful at optimizing the statuses of 25(OH)VD [biological signatures] and simultaneously decreasing TNF- α and IR [functional or clinical outcomes], suggesting a better therapeutic approach compared with supplementation with VD alone in AA subjects.

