2.0 Background*

Previous human studies report that VD supplementation increases circulating 25(OH)VD status but has limited success in reducing insulin resistance (IR). Other human studies report that supplementation with LC lowers TNF- α and IR. This clinical trial will determine the impact of combined supplementation with VD+LC on increases in levels of 25(OH)VD as well as simultaneous reduction in TNF- α and IR biomarkers (mediators of clinical benefit) in the AA population. The mechanistic focus of this clinical trial will determine whether combined supplementation with VD and LC provides a more successful approach to increasing 25(OH)VD [biological signatures] as well as simultaneously decreasing TNF- α and IR [functional or clinical outcomes], compared with supplementation with VD alone. If the results are positive, future studies will investigate potential of this approach to reduce the inflammation, pain, and other health issues among AA in a full-scale efficacy trial.

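### The 30 completers per group are justified only by a within-arm paired t-test, not by the VD+LC versus VD comparison the trial is about, and TNF-α, a primary endpoint, has no calculation

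*Protocol*

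**What the plan says.** Section 1.0 sets out to show that VD+LC is more successful than VD at raising 25(OH)VD while lowering TNF-α and IR, "suggesting a better therapeutic approach compared with supplementation with VD alone in AA subjects". Section 2.0 repeats that contrast as the mechanistic focus of the trial. Section 7.0 lists three primary endpoints: 25(OH)VD, TNF-α and HOMA-IR.

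Section 10.0 plans within-group tests of change (Wilcoxon signed-rank or paired t-test), "the ANOVA test to compare the 4 treatment groups on changes", and adjustment for covariates, including initial levels, "by including them in the repeated measures model used".

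The sample-size text in section 10.0 gives two goals for subjects on VD+LC: a mean rise of 30 ng/mL in 25(OH)VD and a 35% reduction in IR. It then says that "a sample size of 7 for 25(OH)VD, and 27 for IR were considered adequate using a paired" t-test at the 5% level with 80% power, and continues: "We chose a goal of 30 subjects in each group who complete the study". It goes on to treat 30 per group (120 in all) as the required number. It gives no SD, no sidedness, no expected response under VD alone and no between-arm difference, and it does not mention TNF-α.

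**The concern.** A significant fall in IR within the VD+LC arm cannot show that LC adds anything to VD. That takes a comparison of two arms, which differs from the paired test in two ways. With the same SD of change, the difference between two arm means has twice the variance of one arm's mean change. And if VD alone has any effect, the difference to be detected is smaller than the within-arm change assumed in section 10.0.

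The reader is therefore told that 30 per group is required, but cannot tell whether it is enough for the trial's own question on IR or TNF-α. Section 2.0 makes further study of this approach, up to a full-scale trial, depend on positive results here, so a true difference that is missed would have consequences.

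**Working it through.** **Inputs from the protocol.** Paired t-test, α = 0.05, power 80%; n = 7 for 25(OH)VD and n = 27 for IR; goals of 30 ng/mL and 35%; 30 completers per arm (section 10.0). Five clinic visits ("willing to participate in 5 clinic visits where blood will be drawn", section 3.0) less screening and baseline leave three post-baseline visits, which agrees with the four time points in section 10.0.

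**Assumptions.** The two goals were the effects used for 7 and 27 (the natural reading, though not stated outright); two-sided tests; the same SD of change in both arms.

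**1. The plan's own figures.** Without an SD, 7 and 27 cannot be reproduced forwards. Solving the noncentral t for the standardised change d that gives 80% power:
- n = 27: d = 0.560, so the implied SD of IR change is 35/0.560 = 62.5 percentage points.
- n = 7: d = 1.273, so the implied SD of 25(OH)VD change is 30/1.273 = 23.6 ng/mL.

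**2. The same SDs in an unadjusted two-group test, 30 per arm.** The noncentrality is (difference/SD) × √(30/2). For the full IR difference it is 0.560 × 3.873 = 2.17 on 58 df.

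| VD+LC minus VD, as a share of the goal | IR power | 25(OH)VD power |
|---|---|---|
| full (35 points; 30 ng/mL) | 0.57 | 0.998 |
| three-quarters | 0.36 | 0.95 |
| half | 0.19 | 0.68 |

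The full difference corresponds to no effect of VD alone. For 80% power this test needs a difference of 0.736 SD, which is 46 points for IR and 17.3 ng/mL for 25(OH)VD. The latter is 17.3/30 = 58% of the goal, so VD alone may produce up to about 42% of the rise. The paired test at n = 30 needs only 0.529 SD.

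**3. Allowing for the planned model (IR).** Assume compound symmetry with correlation ρ and per-visit variance s² = 62.5²/(2(1−ρ)). The baseline-adjusted variance is s²(1−ρ²) for a single visit and s²((1+2ρ)/3 − ρ²) for the mean of three visits. Residual df are pooled over four arms.

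| Analysis and effect | ρ = 0.3 | ρ = 0.5 | ρ = 0.7 |
|---|---|---|---|
| Last visit, 35 points | 0.76 | 0.70 | 0.65 |
| Mean of three visits, constant 35 points | 0.97 | 0.92 | 0.85 |
| Mean of three visits, constant three-quarters of 35 | 0.82 | 0.71 | 0.61 |
| Mean of three visits, constant half of 35 | 0.48 | 0.39 | 0.32 |
| Mean of three visits, effect building linearly to 35 | 0.72 | 0.60 | 0.51 |

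**4. Sensitivity to how 7 and 27 arose.** If n = 27 came from a normal approximation, from rounding up, or from a one-sided plan with a one-sided between-arm test, the 0.57 becomes 0.54 to 0.59. A one-sided plan followed by a two-sided between-arm test gives about 0.45 to 0.47. For 25(OH)VD the 58% becomes 51% to 69%, or up to about 78% if n = 7 came from a one-sided normal approximation and the between-arm test is two-sided.

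**5. TNF-α.** Neither an effect nor an SD is stated, so nothing can be computed.

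**The case against.** The paired test is one of the planned analyses, and the 30 ng/mL and 35% goals are within-arm goals. Section 10.0 attaches its 80% power to that test and never claims it for VD+LC versus VD. So 7 and 27 may be right for what they describe. That stands: the sums are not shown to be wrong.

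Nor is 30 per arm shown to be too few. Every SD above is back-solved, and the correlations and effect shapes are assumed. Section 2.0 reports limited success of VD alone in reducing IR, so a contrast near the full 35 points is the case closest to the protocol, and some model-based scenarios then exceed 80%. This also stands, and it is why the conclusion is a missing justification rather than proven inadequacy. Modest power can be a reasonable choice in a mechanistic trial that precedes a larger one, but it should be stated.

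Finally, SD source, scale and time point are often left to an analysis plan. That carries less weight here. The protocol chose to justify its sample size and did so on a contrast other than its hypothesis.

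**Conclusion.** The point holds and should be fixed. Confidence is high that the justification does not match the trial's question and that TNF-α is left out, because both follow from the text alone. Confidence in the sizes is low to moderate.

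- **IR:** under the SD implied by n = 27, power for a full 35-point advantage over VD is about 57% unadjusted, and 51% to 97% across the model-based scenarios for the same final difference. Whether 30 per arm reaches 80% depends on the SD, the VD-alone response and the time point, none of which the sample-size text states.
- **25(OH)VD:** 30 per arm is adequate unless VD alone gives roughly 40% or more of the 30 ng/mL rise. That threshold is lower if n = 7 came from a one-sided calculation.
- **TNF-α:** adequacy is unknown.

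**What to change.** In section 10.0, state that 7 and 27 size only the change within the VD+LC arm. Then justify 30 completers per arm on VD+LC minus VD in change, under the planned model and at a named time point or average over visits. For each of 25(OH)VD, HOMA-IR and TNF-α give:
- the SD and scale, from the sponsor's own data;
- the assumed response under VD alone;
- the sidedness of the test;
- the resulting detectable difference and power.

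Do not present 30 per arm as having 80% power for the IR contrast unless that calculation supports it. The back-solved figures here are illustrations and should not be carried into the protocol.

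The cost is protocol wording and one recalculation. No subjects are added and the planned methods stay as they are, although naming a time point settles something section 10.0 leaves open and must agree with any analysis plan. The stated power for IR may turn out less favourable.
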